9.5.4.2 Reporting of Pregnancy and Exposure to Study Drug Through Breastfeeding

Any pregnancy in a female subject in which the estimated date of conception is either before the last visit or within 28 days of the last study treatment or any exposure to the study drug through breastfeeding during study treatment or within 28 days of the last study treatment must be reported.

If an adverse outcome of a pregnancy is suspected to be related to study drug exposure, this should be reported regardless of the length of time that has passed since the exposure to study treatment.

A congenital anomaly, death during the perinatal period, an induced abortion, or a spontaneous abortion is considered to be an SAE and should be reported in the same time frame and in the same format as all other SAEs (see Section 9.5.4.1).

Pregnancies or exposure to the study drug through breastfeeding must be reported by fax or email as soon as possible but no later than 1 business day from the date the investigator becomes aware of the pregnancy. The contact information for the reporting of pregnancies and exposure to the study drug through breastfeeding is provided in Attachment 1. The Pregnancy Report Form (Attachment 4) must be used for reporting. All pregnancies must be followed to outcome. The outcome of the pregnancy must be reported using the Pregnancy Outcome Report Form (Attachment 5) as soon as possible but no later than 1 business day from the date the investigator becomes aware of the outcome.

A subject who becomes pregnant must be withdrawn from the study.

9.5.4.3 Reporting of Events Associated With Special Situations

9.5.4.3.1 REPORTING OF ADVERSE EVENTS ASSOCIATED WITH STUDY DRUG OVERDOSE, MISUSE, ABUSE, OR MEDICATION ERROR

Adverse events associated with study drug overdose, misuse, abuse, and medication errors refer to AEs associated with uses of the study drug outside of that specified by the protocol. Overdose, misuse, abuse, and medication errors are defined as follows:

Overdose	Accidental or intentional use of the study drug in an amount higher than the protocol-defined dose
Misuse	Intentional and inappropriate use of the study drug not in accordance with the protocol
Abuse	Sporadic or persistent intentional excessive use of the study drug accompanied by harmful physical or psychological effects
Medication error	Any unintentional event that causes or leads to inappropriate study drug use or subject harm while the study drug is in the control of site personnel

All AEs associated with overdose, misuse, abuse, or medication errors should be captured on the Adverse Event CRF and also reported using the procedures detailed in Section 9.5.4.1 even if the AEs do not meet serious criteria. Abuse is always to be captured as an AE. If the AE associated with an overdose, misuse, abuse, or medication error does not meet serious criteria, it must still be reported using the SAE form and in an expedited manner but should be noted as nonserious on the SAE form and the Adverse Event CRF.

9.5.4.3.2 REPORTING OF STUDY-SPECIFIC EVENTS

In this study, adverse events associated with renal dysfunction and adverse events associated with anaphylaxis will be handled as “adverse events of special interest (AESIs)”

(see Section 9.5.1.5.3).

If an adverse event of special interest associated with renal dysfunction, with an elevated creatinine level $>3\times$ the upper limit of normal (ULN), or an adverse event associated with anaphylaxis (regardless of severity) is observed, it will be reported according to the procedures specified in “Reporting of Serious Adverse Events” (Section 9.5.4.1) even if the AEs do not meet serious criteria. If the event does not meet the definition of a SAE, it must still be reported using the SAE form and in an expedited manner but should be noted as nonserious on the SAE form and the Adverse Event CRF.

9.5.4.4 Expedited Reporting

The sponsor must inform the investigator, the head of the medical institution, and regulatory authorities of reportable events, in compliance with applicable regulatory requirements. For this reason, it is imperative that the investigator provides complete SAE information in the manner described in Section 9.5.4.1 .

9.5.4.5 Breaking the Blind

Not applicable.

9.5.4.6 Regulatory Reporting of Adverse Events

Adverse events will be reported by the sponsor to the regulatory authorities in compliance with regulatory requirements and established guidance. The format of these reports will be dictated by the regulatory requirements.

9.5.5 Completion/Discontinuation of Subjects

A subject may elect to discontinue the study at any time for any reason. The investigator will promptly explain to the subject involved that the study will be discontinued for that subject and provide appropriate medical treatment and other necessary measures for the subject.

All subjects who discontinue the study between the start of the first study treatment (Day 1) and Day 4 are to complete the procedures/assessments at the Early Discontinuation Visit indicated in the Schedule of Procedures/Assessments (Table 2). In addition, when the discontinuation has occurred before the start of the study treatment on Day 2, Day 3, or Day 4, the procedures/assessments that had been performed on that day of discontinuation can be deemed to be those at the Early Discontinuation Visit.

Even if the procedures/assessments at the Early Discontinuation Visit have been conducted, the procedures/assessments at the Follow-up Visit designated in the Schedule of Procedures/Assessments (Table 2) will be performed 7 days (allowance window: +7 days) after the last dose of study drug, as far as possible. In addition, between the Early Discontinuation Visit and the Follow-up Visit, the study treatment will be switched back to the original dose of oral perampanel used in the Pretreatment Phase, and a stable dosage of another AED(s) as an adjunctive therapy as well as recording of seizures (recording by

the subjects' caregiver is also acceptable) will be continued, as far as possible. The results of these procedures/assessments and the relevant drug information regarding oral perampanel and the other AED(s) will be recorded in the CRF.

If by any chance the procedures/assessments at the Early Discontinuation Visit cannot be conducted before the Follow-up Visit which is to occur 7 days (allowance window: +7 days) after the last dose of study drug, the procedures/assessments at the Follow-up Visit can be omitted.

A subject who has ceased to return for visits will be followed up by mail, phone, or other means to gather information such as the reason for failure to return, the status of treatment compliance, the presence or absence of AEs, and clinical courses of signs and symptoms.

Subjects who discontinue early from the study will be discontinued for 1 primary reason. In addition to the primary reason, the subject may indicate 1 or more secondary reason(s) for discontinuation. Study disposition information will be collected on the Subject Disposition CRF.

If subjects cannot continue the study drug for any reason(s), they must discontinue the study. In addition, a subject who becomes pregnant must be withdrawn from the study.

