9.5.1.5.3 STUDY-SPECIFIC ADVERSE EVENTS

In a non-clinical toxicity study of sodium sulphobutylether-beta-cyclodextrin (hereinafter “SBECD”), which is one of the additives in this study drug, vacuolation was observed in tubular epithelial cells, suggesting that patients with impaired renal function have a risk of SBECD accumulation (Luke, et al., 2010). In addition, there have been reports of anaphylaxis, possibly due to SBECD, with other formulations containing SBECD.

In this study, based on the above findings, adverse events associated with renal dysfunction, and adverse events associated with anaphylaxis will be handled as “adverse events of special interest (AESIs)” and recorded in the CRF.

For the procedures for reporting adverse events of special interest, see Section 9.5.4.3.2

1. Adverse Events Associated With Renal Dysfunction

If an adverse event associated with renal dysfunction occurs, and does not resolve at the time point when the Follow-up Phase is completed, the investigator will monitor the subject for 14 days from the follow-up visit, regardless of severity, and will continue following up the subject as needed until resolution of the event or, if resolution is unlikely, until stabilization of the symptom or sign. During this period, the subject will be followed up continuously by renal function monitoring at unscheduled visits (eg, once weekly, or at a frequency deemed necessary by the investigator).

2. Adverse Events Associated With Anaphylaxis

In the event of an adverse event associated with anaphylaxis, the investigator will take the following responsive actions:

- Take the first response, for example, by immediately referring the subject to an appropriate clinical department;
- Make a decision regarding whether or not to continue administration of the study drug to the subject, based on advice from the physician in the above-mentioned department;
- In the event of an adverse event associated with anaphylaxis while continuing intravenous administration of the study drug, discontinue the administration. In the event of any symptom or sign that is suspected of anaphylaxis while continuing intravenous administration of the study drug, careful judgment will be exercised in determining whether or not to continue the administration.

The follow-up of anaphylaxis will be continued until resolution of the event or, if resolution is unlikely, until stabilization of the symptom or sign.

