9.5.2 Schedule of Procedures/Assessments

9.5.2.1 Schedule of Procedures/Assessments

Table 2 presents the schedule of procedures/assessments.

Table 2 Schedule of Procedures / Assessments in Study E2007-J081-240

Phase	Pretreatment Phase		Treatment Phase ^a				Follow-up Phase ^{b, c}	Unscheduled Visit ^k	Early Discontinuation Visit
	Day -28 to -7 (Screening)	Day -1	Day 1	Day 2	Day 3	Day 4			
Study Day(s) (from Day 1 of Treatment Phase)							7 days after the last intravenous infusion		
Visit	1	2	3a	3b	3c	3d		4	
Procedure/Assessment									
Informed consent/assent ^d	X								
Inclusion/exclusion criteria	X	X	X						
Physical examinations	X	X	X ^m	X ^m	X ^m	X ^m	X	X	X
Medical history	X								
Concomitant medications/therapies	X ^e	X ^e	X ^e	X	X	X	X	X	X
Hospitalization		X	X	X	X	X ^l			
Intravenous administration of the study drug (intravenous infusion of perampanel)			X	X ⁿ	X ⁿ	X ⁿ			
Oral perampanel administration at the hospital		X ⁿ							
Adverse events ^f	X	X	X	X	X	X	X	X	X
Oral perampanel/study drug compliance	X	X	X	X	X	X	X		X
Dispense subject diary	X		X			X			X
Return and review subject diary			X			X	X ^o		X
Discontinuation/continuation judgment ^g		X	X	X	X	X			
Vital signs and weight/height ^h	X	X	X ^m	X ^m	X ^m	X ^m	X	X	X
Clinical laboratory evaluations	X	X				X ^m	X	X	X
PK blood sampling for perampanel ⁱ		X	X	X	X	X			
Urine drug screen	X								
Urine pregnancy test ^j		X					X	X	X
Serum pregnancy test ^j	X							X	
12-lead ECG	X	X				X ^m	X	X	X

- a: The date of each visit to be specified based on the date of Visit 3a. The Treatment Phase is defined as the period beginning at the start of the study treatment (intravenous infusion of perampanel) on Day 1 to immediately before the oral perampanel administration on Day 5.
- b: Visit to be performed within +7 days of the schedule. The visit is to be specified based on the date of the last intravenous infusion of perampanel.
- c: To be completed by subjects who received at least 1 intravenous infusion of perampanel, in principle.
- d: Informed consent must be obtained before any study-related procedure.
- e: Prior and concomitant medication(s)/therapies(s).
- f: Adverse events will be collected from the time the subject signs the informed consent form through the 21 days after the subject's last intravenous infusion of perampanel. Serious adverse events will be collected for 28 days after the subject's last intravenous infusion of perampanel.

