9.7.1.8.3 LABORATORY VALUES

Laboratory results will be summarized using Système International (SI) units, as appropriate. For all quantitative parameters, the actual value at each visit and the change from baseline to each postbaseline visit will be summarized using descriptive statistics. Qualitative parameters will be summarized using frequencies (number and percentage of subjects), and changes from baseline to each postbaseline visit will be reported using shift tables. Percentages will be based on the number of subjects with both nonmissing baseline and relevant postbaseline results.

Laboratory test results will be assigned a low/normal/high (LNH) classification according to whether the value was below (L), within (N), or above (H) the laboratory parameter's reference range. Within-treatment comparisons for each laboratory parameter will be based on shift tables that compare the baseline LNH classification to the LNH classification at each postbaseline visit.

Appendix 1 (Sponsor's Grading for Laboratory Values) presents the criteria that will be used to identify subjects with treatment-emergent markedly abnormal laboratory values (TEMAVs). Except for phosphate, a TEMA V is defined as a postbaseline value with an increase from baseline to a grade of 2 or higher. For phosphate, a TEMA V is defined as a postbaseline value with an increase from baseline to a grade of 3 or higher. The definition of TEMA V will be detailed in the SAP. When displaying the incidence of TEMAVs, each subject may be counted once in the laboratory parameter high and in the laboratory parameter low categories, as applicable.

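### The waiver in Protocol 9.5.5 lets the Follow-up Visit be dropped when the Early Discontinuation Visit was not held in time, without requiring a late visit in its place

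*Protocol*

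**What the plan says.** Section 9.5.5 sets out four rules for subjects who stop early.

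- General duty: "All subjects who discontinue the study between the start of the first study treatment (Day 1) and Day 4 are to complete the procedures/assessments" of the Early Discontinuation (ED) Visit.
- Same-day substitution: if the subject stops before the infusion on Day 2, 3 or 4, "the procedures/assessments that had been performed on that day of discontinuation can be deemed to be those at the Early Discontinuation Visit".
- ED Visit done: "Even if the procedures/assessments at the Early Discontinuation Visit have been conducted, the procedures/assessments at the Follow-up Visit" are still performed, 7 days (+7 days) after the last dose, as far as possible.
- ED Visit not done in time: "If by any chance the procedures/assessments at the Early Discontinuation Visit cannot be conducted before the Follow-up Visit", then "the procedures/assessments at the Follow-up Visit can be omitted".

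Three other places bear on this. Table 2, footnote c, says of the Follow-up Visit: "To be completed by subjects who received at least 1 intravenous infusion of perampanel, in principle". Section 9.5.1.5.3 says that for a renal event still unresolved at the end of the Follow-up Phase, "the investigator will monitor the subject for 14 days from the follow-up visit, regardless of severity". Section 9.7.1.8.3, after describing the shift tables for qualitative laboratory parameters, says: "Percentages will be based on the number of subjects with both nonmissing baseline and relevant postbaseline results".

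**The concern.** The last two rules work against each other. The subject who already has one post-infusion assessment is asked for a second; the subject who has none may be excused. The waiver names no replacement visit, sets no deadline for a late ED Visit and keeps no minimum set of tests.

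The primary objective is the safety and tolerability of the infusion, and subjects who stop early are among the most informative for it. Anyone who cannot continue the infusion must leave the study (sections 9.1.2 and 9.5.5), so a subject who stops between Day 1 and Day 4 comes under these rules. Renal dysfunction is an adverse event of special interest because of an excipient (9.5.1.5.3), and a creatinine rise without symptoms would not come to light in a telephone call about adverse events. Section 9.7.1.1 makes no adjustment for missing data, so what is not measured is simply absent from the tables.

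**Working it through.** The plan gives no figure to reproduce, and the sample size rests on feasibility. The check is a reading of 9.5.5 against Table 2.

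**When laboratory tests and ECG are scheduled (Table 2).** Screening, Day -1, Day 4 (predose, footnote m), Follow-up and ED. The Unscheduled Visit column lists them too, but only as the investigator judges necessary (footnote k). After the first infusion, the scheduled occasions are therefore Day 4 predose, ED and Follow-up. Vital signs, weight and physical examination are also done predose on each of Days 1 to 4.

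**What each route through 9.5.5 yields.**

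| Route | Follow-up Visit under 9.5.5 | ED and Follow-up assessments left |
|---|---|---|
| A. ED Visit held on stopping | still due | two |
| B. Stopped before the Day 2 or Day 3 infusion, that day's procedures counted as ED | still due | Follow-up only, for laboratory tests and ECG, since Table 2 schedules none on those days |
| C. ED Visit late, but held | may be omitted | one |
| D. ED Visit never held | may be omitted | none |

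Routes A to C are satisfactory. Route D is the gap: it departs from the general duty to complete the ED Visit, but the waiver still applies to it as worded.

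**What is lost on route D.**

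- Last infusion on Day 1, 2 or 3, and gone before the Day 4 predose examinations: laboratory tests and ECG exist only from Screening and Day -1, so there are 0 scheduled results after any infusion.
- Last infusion on Day 4: one set, taken after three infusions, and none after the fourth.

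**What remains on route D.** Adverse events to 21 days and serious adverse events to 28 days after the last infusion (9.5.1.5.1; Table 2, footnote f). Seizure counts to 14 days, with diary recording as far as possible (footnote o). Mail or telephone contact for subjects who stop attending (9.5.5). Plasma samples, vital signs, weight and physical examination from treatment days already attended.

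**Do the ED and Follow-up columns differ?** Both list physical examination, concomitant medications, adverse events, compliance, diary return, vital signs and weight, laboratory tests, urine pregnancy test and ECG. Only the ED column also lists dispensing a diary. One visit can therefore meet both.

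**Size.** One subject is 1/20 = 5% of the planned sample. As an illustration only, assume that 2 of 20 subjects take route D before Day 4 and that 1 of them has a markedly abnormal creatinine. If only subjects with a postbaseline result are counted, the table reads 0/18 = 0% instead of 1/20 = 5%. With 1 or 3 such subjects lost, it reads 0/19 or 0/17, again 0% against 5%. The plan gives no expected number of early stoppers, so these counts have no source in it.

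**The case against.** The strongest reply is that the sentence must be read with the rest of 9.5.5. Its trigger is timing: the ED Visit cannot be held *before* the Follow-up Visit. The duty to complete the ED Visit is not withdrawn; only the Follow-up procedures are released. On that reading, an ED Visit that slips into the Follow-up window simply makes a near-identical second visit unnecessary. This is probably what was meant, but the text does not say it. A site that never holds the ED Visit and then omits the Follow-up Visit can point to a stated permission for the omission.

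A reader might infer that such a subject has no post-infusion assessment at all. The documents do not support that: adverse event collection, seizure recording, remote contact and predose measurements on attended days continue, and tests at unscheduled visits are possible.

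A reader might also see a flat contradiction with footnote c. That footnote is stated only in principle, which leaves room for an exception. The two fit badly but are not irreconcilable. Nor does a known renal event go unfollowed: 9.5.1.5.1 and 9.5.1.5.3 require follow-up to resolution or stabilization whatever the visit date.

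The case is also likely to be uncommon. Subjects are inpatients during the infusions, the sentence itself treats the situation as exceptional, and same-day substitution means that many who stop before an infusion will count as having had the ED Visit. All of that stands, and it limits how often the gap opens. It does not alter what the sentence permits.

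**Conclusion.** The point holds as a defect of wording with a real consequence. As written, the waiver lets both post-infusion visits be missed. A subject who stops before the Day 4 predose examinations could then contribute no scheduled creatinine, other laboratory result or ECG after any infusion. This rests on Table 2 as printed and on a literal reading of the waiver; if sites take a late ED Visit as the substitute, nothing is lost.

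Each affected subject is 5% of the planned 20. How many there would be cannot be derived from the protocol, and the 0/18 against 1/20 comparison is an assumed illustration. Its denominator is assumed too: the sentence on percentages follows the qualitative shift tables, and the detailed definition of markedly abnormal values is left to the SAP. It would be tempting to conclude that the missing results bias the safety tables in favour of the infusion. That would require the missing results to be worse than the observed ones, which the documents do not show.

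The sentence should be amended: this is a stated permission that works the wrong way in a trial whose primary objective is safety.

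**What to change.** Replace the waiver sentence in 9.5.5 with:

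> If the ED procedures cannot be conducted before the Follow-up Visit, a single visit 7 days (+7 days) after the last infusion will be performed, as far as possible, and will serve as both the ED and the Follow-up Visit.

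This brings 9.5.5 into line with footnote c and with the probable intent, and it respects a subject's right to withdraw. Section 9.5.1.5.3, which counts renal monitoring from the follow-up visit, has no start date when that visit is omitted; it should be reconciled with 9.5.5.

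The cost is one sentence in a protocol amendment, plus that reconciliation. No procedure or visit window is added. The small downside is the effort for sites to bring back a few subjects who stopped early.

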9.5.6 Abuse or Diversion of Study Drug

Not applicable.

9.5.7 Confirmation of Medical Care by Another Physician

The investigator or the designated investigator's staff will instruct the subjects and the subjects' legally acceptable representatives (if applicable) to inform site personnel when the subjects are planning to receive medical care from another physician. At each visit, the investigator or the designated investigator's staff will ask the subject and the subject's legally acceptable representative (if applicable) whether the subject has received medical care by another physician since the last visit or is planning to do so in the future. When the subject is going to receive medical care by another physician, the investigator, with the consent(s) of the subject and the subject's legally acceptable representative (if applicable), will inform the other physician that the subject is participating in the clinical study.

9.6 Data Quality Assurance

This study will be organized, performed, and reported in compliance with the protocol, SOPs, working practice documents, and applicable regulations and guidelines.

9.6.1 Data Collection

Data required by the protocol will be collected on the CRFs and entered into a validated data management system that is compliant with all regulatory requirements. As defined by J-GCP guidelines, the CRF is a printed, optical, or electronic document designed to record all of the protocol-required information to be reported to the sponsor on each study

subject.

Data collection on the CRF must follow the instructions described in the CRF Completion Guidelines. The investigator has ultimate responsibility for the collection and reporting of all clinical data entered on the CRF. The investigator must sign the completed CRF to attest to its accuracy, authenticity, and completeness.

Completed, original CRFs are the sole property of Eisai and should not be made available in any form to third parties without written permission from Eisai, except for authorized representatives of Eisai or appropriate regulatory authorities.

